8. CORRELATIVE/SPECIAL STUDIES

8.1. Laboratory Correlative Studies

Correlatives studies will be done, utilizing research samples collected on this study that will primarily focus on biomarkers of prognosis or prediction of therapeutic benefit based on current or future scientific evidence.

8.1.1. Collection of Specimens

Blood specimens will be collected for the purpose of laboratory corollary studies as follows:

Table. Blood sample Collection				
Course 1	Red Top Tubes²	Green Top Tubes³	PAX tubes⁴	Yellow Top Tube⁵
Baseline ¹	3	10	1	1
Cycle 2 of IL-2, within 1-3 weeks after the last dose of IL-2	3	10	1	none

Course 2/3				
Cycle 2 of IL-2, within 1-3 weeks after the last dose of IL-2	3	10	1	none
Month 12	3	10	1	none
Progression	3	10	1	none
1. Baseline: within 2 weeks of the first dose of IL-2. 2. 10 cc RED top tubes (BDcat #367820 or SST 367988 gel separator/gold top/ tiger tubes if the center can centrifuge them) 3. 10 cc GREEN top tubes (BD cat # 366480) 4. PAX tube (Fisher #23 021 01) 5. 10 cc YELLOW top tube. (BD cat # 364606)				

Transfer or, if applicable, ship blood samples by overnight courier Monday-Thursday only to:

Immunologic Monitoring and Cellular Products Laboratory
 University of Pittsburgh Cancer Institute
 UPCI-IMCPL, Suite 1.26
 Study Coordinator
 Hillman Cancer Center
 [name]
 [name]
 [contact]
 [contact]

Please submit the Specimen Submission Form (template to be provided separately) for each sample sent.

Notify the IMCPL study coordinator by [contact]) when the samples are shipped. If you are unable to get through to the laboratory by fax, telephone the study coordinator and provide the tracking number.

The IMCPL has a great deal of experience in shipment and handling of blood, tumor and lymph node samples. The IMCPL provides contact information and a fax request form to the sites, and when a patient is scheduled, a tissue sample kit is shipped (generally via ground) to the site, containing all necessary blood tubes, tumor containers (containing sterile medium) sample instructions as well as return overnight shipping instructions. Upon receipt in the laboratory, the blood and tissue samples are logged in a processed according to the protocol-specific SOPs. Samples which are compromised (hemolyzed or which arrived more than 48 hours after draw/isolation) are discarded (currently less than 2% of >750 samples which arrive at the laboratory annually from ECOG-ACRIN sites).

Pathology Specimen Submissions for Banking for Research Studies (at baseline, then at disease progression):

- Primary Melanoma (for patients with known primary cutaneous melanoma)
Fifteen (15) unstained slides preferably from the thickest portion of the tumor for immunostains (please do not deparaffinise slides) OR, if the primary pathologist is willing, please request the corresponding block, which will be promptly returned upon request. If the patient has more than one primary lesion, please include above slides and/or block for each primary.
- Resected in-transit or satellite metastases, or cutaneous metastases, or lymph node metastases, or lung metastases
Fifteen to twenty (15-20) unstained slides from the thickest part of the tumor or, if the primary pathologist is willing, please request the corresponding block, which will be promptly returned upon request.

NOTE: Please provide a surgical pathology report to accompany the slides.

- Progression/Relapse Biopsy (if performed, for banking for future research)
Fifteen to twenty (15-20) unstained slides from the thickest part of the tumor or, if the primary pathologist is willing, please request the corresponding block, which will be promptly returned upon request.

Please transfer or, if applicable, ship to the IMCPL, as noted above. For shipping, regular mail may be used for these tissue samples OR these may be included in the same package with the blood samples shipped by overnight courier. Also please notify the IMCPL study coordinator as noted above.

NOTE: Patients who do not have archival tumor (as part of a standard of care procedure) available for research at baseline or at progression will be asked whether they are willing to provide a biopsy for research in case they have an accessible tumor for a punch biopsy in clinic.

8.1.2. Banking of Specimens for Future Laboratory Corollary Studies

Specimens will be banked and laboratory corollary studies will be conducted based on the availability of specimens and funding.

9. STUDY CALENDAR

Study investigators should follow the local institutional standard of care guidelines for safety monitoring and safety laboratory testing. Baseline evaluations are to be conducted within 2 weeks prior to administration of HD IL2, unless indicated otherwise, elsewhere in the protocol. Scans and X-rays must be done not more than 28 days prior to the start of HD IL2. In the event that the patient's condition is deteriorating, laboratory evaluations should be repeated within 48 hours prior to initiation of the next cycle of IL2.

Course 1	Pre-Study	Wk 1	Wk 2	Wk 3	Wk 4	Wk 5	Wk 6	Wk 7	Wk 8	Off Study ^f
Interleukin-2 ^a		X		X						
Informed consent	X									
Demographics	X									
Medical history	X									
Concurrent meds	X	X-----X								
Physical exam	X	X		X						X
Vital signs	X	X		X						
Height	X									
Weight	X	X		X						
Performance status	X	X		X						X
CBC w/diff, plts Urinalysis	X	X		X						X
Serum chemistry	X	X		X						X
PT/INR	X									
Cardiac stress test ^b	X									
PFTs ^c	X									
Adverse event evaluation		X-----X								
Tumor measurements	X								X	X
Radiologic evaluation ^d	X								X	X
B-HCG ^e	X									
Research Biospecimen	See Section 8.1.1									

- a: IL-2: 600,000 U/kg/dose IV Q8h x 5 days (max 14 doses) starting on day 1 of weeks 1 and 3. An IL-2 cycle may be delayed until the resolution of limiting toxicities.
- b: Patients who are over 40 years old or have had previous myocardial infarction greater than 6 months prior to study entry or have significant cardiac family history (CAD or serious arrhythmias) will be required to have a negative or low probability cardiac stress test (thallium stress test, stress MUGA or exercise stress test) for cardiac ischemia within 8 weeks prior to registration. Patients who are not required to have a cardiac stress test should have an electrocardiogram at baseline to be reviewed by the treating physician investigator. Patients who undergo echocardiography as part of their cardiac stress test are not required to have a separate baseline echocardiogram.
- c: Pulmonary function tests (PFTs) are required for patients over 50 years old or with significant pulmonary or smoking history. PFTs may be done up to 4 weeks prior to registration.
- d: Radiologic evaluation should include MRI or contrast CT of the brain at baseline and may be repeated at later time points as clinically indicated.
- e: Serum pregnancy test (women of childbearing potential).
- f: Off study evaluation. Patients will be followed for 5 years after removal from study or until death, whichever occurs first. The frequency and the type of evaluations during this follow up period will follow institutional standard of care practices. For patients who wish not to follow with a study investigator, they can be followed by their treating physician of choice and also following local standard of care practices. Data on disease progression and survival will be collected on all patients every 3-6 months.

For the purposes of this study, patients should be reevaluated for response at the end of each course 1 (8 weeks +/- 1 week). Following completion of treatment, and in the absence of disease progression will be done every 12 weeks +/- 2week during the observation phase for the first 2 years, then every 6 months (-/+ 2 weeks) for years 3-5, then yearly (-/+ 4 weeks) afterwards.

MRI or contrast CT of the brain is not required but should be done as clinically indicated. For those subjects who have progressed, Data on survival will be collected on all patients every 6months for 5 years.

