5. TREATMENT PLAN

5.1. Overall Treatment Plan

This is a phase II study of high dose bolus interleukin-2 (HD IL2) in patients with advanced inoperable stage III or stage IV melanoma who have prior anti-PD1 immunotherapy.

Definitions:

1. A cycle of IL-2: eligible patients receive HD IL2 at 600,000 IU/kg IV every 8 hours for up to 14 doses. This constitutes one cycle of IL2.

2. Each course consists of 2 cycles of HD IL2 as follows: high-dose IL2 at 600,000 IU/kg is given IV every 8 hours for up to 14 doses (one cycle), followed by a rest period of 1-2 weeks and readmission for a second HD IL2 cycle for up to 14 doses (2nd cycle).
3. Based on the occurrence of treatment-related toxicities and requirements for dose adjustments or delays, a patient may or may not receive the full planned treatment, but response assessment will continue to be carried out at the end of each course.

The planned treatment consists of 3 courses (6 cycles) of HD IL-2. Response assessment will occur at the end of each course of therapy and patients without evidence of disease progression (RECIST v.1.1) or limiting toxicities will be offered additional courses of treatment of HD IL2 for a maximum of 3 courses.

	Course of HD IL2*							
	Wk 1	Wk 2	Wk 3	Wk 4	Wk 5	Wk 6	Wk 7	Wk 8
HD IL-2 600,000 U/kg/dose IV Q8h x 5 days (max 14 doses)	X		X					
Response Assessment								X

*Local variations are allowed as per local site standard practice, patient recovery from adverse events and scheduling requirements.

Patients will receive HD IL-2 following the institutional standard of care guidelines. Patients will receive a maximum of 3 courses (6 cycles; 1 course of IL2 = 2 cycles of IL2). Response assessment will be carried out at the end of each course. In the absence of disease progression by RECIST v.1.1, patients will be offered additional courses of therapy for a maximum of 3 courses (6 cycles).

Research biospecimens will be collected at the multiple time points as noted in section 8.1.1.

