5.5. Duration of Follow Up

Patients will be followed for 5 years after removal from study or until death, whichever occurs first. Patients removed from study for unacceptable adverse events will be followed until resolution or stabilization of the adverse event. The frequency and the type of evaluations during this follow up period will follow the Study Calendar. For patients who complete the study procedures wish not to have long term follow up with a study investigator, they can be followed by their treating physician of choice and also following local standard of care practices. Data on disease progression and survival for these patients during long term follow up will be collected on all patients every 3-6 months.

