10. MEASUREMENT OF EFFECT

10.1. Antitumor Effect – Solid Tumors

For the purposes of this study, patients should be reevaluated for response as noted in Section 9.

Response and progression will be evaluated in this study using the new international criteria proposed by the Response Evaluation Criteria in Solid Tumors (RECIST v1.1) Committee, version 1.1[Eur J Cancer, 2009. **45**(2): p. 228-47.]. Changes in only the largest diameter (unidimensional measurement) of the tumor lesions are used in the RECIST criteria. See Eisenhauer et al. New response evaluation criteria in solid tumours: revised RECIST guideline (version 1.1). Eur J Cancer. 2009 Jan;45(2):228-47.

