10.1.3. Progression-Free Survival

PFS is defined as the duration of time from start of treatment to time of progression (or death if there is no progression date). Patients with neither a progression date nor date of death will be censored as of last contact.

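### Section 9 gives two unreconciled follow-up rules for progression-free patients off treatment, so scan timing for PFS and response duration can be left to local practice

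*Combined protocol and SAP*

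**What the plan says.** All the relevant text is in the combined protocol and SAP.

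- **Section 9, footnote f.** The footnote sits on the Off Study column, in which tumour measurements and radiologic evaluation are marked. It covers five years after removal from study and says "The frequency and the type of evaluations during this follow up period will follow institutional standard of care practices". It lets any patient who prefers it be followed by a physician of choice, and adds "Data on disease progression and survival will be collected on all patients every 3-6 months".
- **Section 9, next paragraph.** "Following completion of treatment, and in the absence of disease progression will be done every 12 weeks +/- 2week during the observation phase" applies for the first two years, then six-monthly for years 3–5. Patients who have progressed are followed for survival only.
- **Section 10.1.** "For the purposes of this study, patients should be reevaluated for response as noted in Section 9".
- **Section 5.5.** "The frequency and the type of evaluations during this follow up period will follow the Study Calendar". Its local-physician option is narrower than footnote f's: "For patients who complete the study procedures wish not to have long term follow up with a study investigator".
- **Section 5.1, definition 3.** A patient may not receive all planned treatment, but "response assessment will continue to be carried out at the end of each course".
- **Section 10.1.3.** "Patients with neither a progression date nor date of death will be censored as of last contact".
- **Section 11.3.4.** PFS runs to documented progression or death. The percentage progression-free is to be reported at time points such as 3, 6, 12 and 18 months.

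**The concern.** The two rules in Section 9 overlap for a patient who is off treatment and has not progressed. One leaves frequency to the institution and the other fixes it. The 12-week sentence is triggered by completing treatment, which is not defined; footnote f is triggered by removal from study. Section 5.4 lists several reasons for stopping other than progression, toxicity among them, so such patients are to be expected. A site that puts an early stopper under footnote f can claim compliance, and so can a site that scans every 12 weeks.

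Progression is dated when it is documented, so a longer interval dates it later. Censoring at last contact adds to this: a patient who is in contact but not scanned continues to count as progression-free. Response duration depends on scan timing in the same way. Scans that were never done cannot be recovered at analysis, and the planned confidence limits do not reflect this kind of error.

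**Working it through.** **1. The plan's own figure.** The only stated power is for response (Section 11.2): 45 evaluable patients, 20% against 7%, one-sided exact binomial test, alpha 0.10. Rejecting at 6 or more responses gives exact alpha 0.0923 and power 0.910, which agrees with the stated figure of more than 90%. Follow-up intervals do not enter it. The plan has no planning figure for PFS.

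**2. Does another section settle precedence?** Section 5.5 sends the reader back to the calendar, which holds both rules. Section 10.1 echoes the opening of the 12-week paragraph and so favours it, but refers to Section 9 as a whole. Section 5.1 ties assessments to the end of a course, and a patient who has stopped has no further course. None of these overrides footnote f.

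**3. Size of the upward shift.**

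From the documents: scans at weeks 8, 16 and 24 on treatment and every 12 weeks afterwards; 6 months = 26.1 weeks.

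Assumed, not in the documents:
- true PFS S(t) is exponential with median 2–6 months;
- a share s of progression-free patients stops after each course;
- a share q of patients is on a local interval of 19–26 weeks;
- patients remain in contact, and progression is found only at scans.

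A patient who stops after course 1 has the last scan before 6 months at week 20 under the 12-week rule, but at week 8 under a 19–26 week interval. Patients who stop after course 2 (last scan week 16) or finish course 3 (week 24) are the same under both. Hence

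shift = q × s × [S(8) − S(20)].

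With q = 0.25, in percentage points:

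| Median PFS (months) | S(8) | S(20) | Difference | s = 10% | s = 30% | s = 50% |
|---|---|---|---|---|---|---|
| 2 | 0.529 | 0.203 | 0.325 | 0.8 | 2.4 | 4.1 |
| 3 | 0.654 | 0.346 | 0.308 | 0.8 | 2.3 | 3.9 |
| 4 | 0.727 | 0.451 | 0.276 | 0.7 | 2.1 | 3.5 |
| 6 | 0.809 | 0.588 | 0.221 | 0.6 | 1.7 | 2.8 |

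Example: with median 3 months and s = 50%, true 6-month PFS is 25.0%, the 12-week rule gives 34.9%, and a quarter of patients on 26 weeks gives 38.8%.

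**4. What shrinks it** (q = 0.25, s = 30–50%).
- If half of progressions surface between scans, the shift halves, to 0.8–2.0 points.
- If the Off Study scan falls 2–8 weeks after the week-8 scan (its timing is not stated), the shift is 0–3.5 points.
- If weeks 16 and 24 are still scanned, the shift is zero.

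**5. A second model.** Here removal is spread over weeks 3–16 with a scan at removal, 10–31% of patients are removed progression-free, and up to half of progressions are found clinically. The shifts below have every early-removed patient on the local interval. The last column divides by 4, because the shift is proportional to the share on local intervals.

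| Local interval (weeks) | All early-removed patients local | A quarter local |
|---|---|---|
| 6–8 | −0.4 to −2.3 | −0.1 to −0.6 |
| 16 | +0.3 to +1.7 | +0.1 to +0.4 |
| 20 | +1.1 to +5.9 | +0.3 to +1.5 |
| 26 | +1.9 to +10.9 | +0.5 to +2.7 |

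**6. Scale.** The 90% half-width near 35% with 45 patients is 1.645 × √(0.35 × 0.65 / 45) = 11.7 points. In the model of step 3 with s = 30–50%, the 12-week rule itself overstates true 6-month PFS by 6.7–10.0 points, and its permitted ±2-week window is worth s × [S(18) − S(22)] = 1.9–3.7 points.

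**7. Response duration.** Take the historical median of 8.9 months (Section 2.2) as 38.7 weeks, exponential with rate λ. The mean lag from progression to the next scan at interval L is L / (1 − exp(−λL)) − 1/λ: 6.2 weeks for L = 12 and 14.0 weeks for L = 26.

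**The case against.** The strongest reply is that the text already has a natural reading. The paragraph after footnote f is the specific rule for tumour reassessment and Section 10.1 repeats its wording, while footnote f is a general note on five-year follow-up. That paragraph sorts patients by whether they have progressed and creates no separate class of early stoppers. This stands as the better reading. It does not remove the conflict, because the footnote is attached to the column in which tumour assessments are marked and nothing says which rule yields. A reader might infer that the protocol exempts early stoppers from 12-week scanning; the documents do not say that either.

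A reader might also infer that the shift could be several points in either direction. That is not supported. Local intervals of 14–18 weeks lower the estimate only if removals are fixed at set times such as week 8, which happens to place a scan just before 6 months. With removals spread over weeks 3–16 the shift is upward. The downward case that remains is scanning every 6–8 weeks, and it is modest.

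Nor is the 3–6 month interval in footnote f an imaging schedule. It governs data collection, so intervals of 19–26 weeks are an assumption about local practice.

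Finally, the effect is small beside sampling error and beside the upward bias of 12-week scanning, and PFS here is a descriptive secondary summary with no test. That stands, and it limits the weight of the point.

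**Conclusion.** The conflict is real and minor. Two rules cover the same patients, and sites can scan at different intervals while each complies. The likely direction of error in 6-month PFS is upward, helped by censoring at last contact: roughly 0 to 4 points with a quarter of patients on intervals of 19–26 weeks, and under 1 point if only about 10% stop early. Larger figures need every early stopper to be on six-monthly scans. These sizes rest on median PFS, stopping share, local share and local intervals, none of which the documents give.

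Only secondary descriptive estimates are touched. A reader who infers a threat to the primary response rate, the stopping rules or the power would be going beyond the documents.

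**What to change.** Amend footnote f, and align Section 5.5, to say that the existing schedule (every 12 ± 2 weeks for two years, then every 6 months) governs tumour assessment until progression for every patient, whether treatment was completed or stopped early and wherever the patient is followed. Institutional practice would then apply only to non-tumour evaluations and to care after progression.

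The schedule alone leaves last-contact censoring in place. So also record the date of the last progression-free scan, and report one sensitivity analysis of PFS, either interval-censored or censored at the last tumour assessment.

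The cost is a short wording change with no new schedule, one extra date to record, one extra analysis, and the need for some sites and local physicians to align follow-up imaging with the 12-week schedule. The change puts every patient on the same rule. It does not remove the upward bias of 12-week scanning or the variation allowed by the ±2-week window.

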10. MEASUREMENT OF EFFECT

10.1. Antitumor Effect – Solid Tumors

For the purposes of this study, patients should be reevaluated for response as noted in Section 9.

Response and progression will be evaluated in this study using the new international criteria proposed by the Response Evaluation Criteria in Solid Tumors (RECIST v1.1) Committee, version 1.1[Eur J Cancer, 2009. **45**(2): p. 228-47.]. Changes in only the largest diameter (unidimensional measurement) of the tumor lesions are used in the RECIST criteria. See Eisenhauer et al. New response evaluation criteria in solid tumours: revised RECIST guideline (version 1.1). Eur J Cancer. 2009 Jan;45(2):228-47.

10.1.1. Definitions

Evaluable for toxicity. All patients will be evaluable for toxicity from the time of their first protocol drug administration.

Evaluable for objective response. Only those patients who have measurable disease present at baseline, have received at least course 1 of therapy, and have had their disease re-evaluated will be considered evaluable for response. These patients will have their response classified according to the definitions stated below. (Note: Patients who exhibit objective disease progression prior to the end of course 1 will also be considered evaluable.)

10.1.2. Duration of Response

Duration of overall response: The duration of overall response is measured from the time measurement criteria are met for CR or PR (whichever is first recorded) until the first date that recurrent or progressive disease is objectively documented (taking as reference for progressive disease the smallest measurements recorded since the treatment started).

The duration of overall CR is measured from the time measurement criteria are first met for CR until the first date that recurrent disease is objectively documented.

Duration of stable disease: Stable disease is measured from the start of the treatment until the criteria for progression are met, taking as reference the smallest measurements recorded since the treatment started.

10.1.3. Progression-Free Survival

PFS is defined as the duration of time from start of treatment to time of progression (or death if there is no progression date). Patients with neither a progression date nor date of death will be censored as of last contact.

11. STATISTICAL CONSIDERATIONS

11.1. Study Design/Endpoints

This is a phase II study of high dose bolus interleukin-2 (HD IL2) in patients with advanced inoperable stage III or stage IV melanoma who have prior anti-PD1 immunotherapy. The safety of HD IL2 is well studied and will be monitored. The focus of the study is to evaluate the efficacy of this HD IL-2 in this specific patient population.

The primary endpoint is (CR+PR) as assessed by RECIST criteria version 1.1. The total accrual goal is 45 patients. We will follow a Bayesian design to establish sequential stopping rules for futility (Thall, Simon and Estey 1995). The expected response rate for this patient population is between 5 and 10%. We would consider the HD IL-2 worth further investigation if a response rate of 20% is achieved. Thus, if there is sufficient evidence that the response rate of the regiment is 7% or less, we will stop the accrual. Let p_0 and p_1 denote the response rate of the standard treatment and the HD IL-2 respectively, by sufficient evidence, we mean that the posterior probability, $\Pr(p_0 + 0.05 > p_1)$, exceeds 85%. Based on the existing data, it is safe to say that the response rate of the studied population under standard care is between 5 and 10%, therefore, we use a Beta(70,930) prior for the standard treatment, which corresponds to a distribution of the response rate centered at 7%. We set a flat prior, Beta(0.4,1.6), for the response rate of HD IL-2.

We will allow the accrual to continue without interruption for the first 10 patients. The stopping boundaries for futility after the “burning period” can be presented as tables of possible outcomes for efficacy as shown in the following table:

Table 1 Bayesian Stopping Rules

Stop the Accrual to if

Responses<=	in No. Pts
1	10-19
2	20-31
3	32-44
4	45

The operating characteristics of this design can expressed in terms of the probability of

stopping the study early when the regimen is effective (i.e. response rate>0.2) and ineffective (i.e. response rate<0.07) and the median sample size under each situation. The following table summarizes this probability and the median sample size under this design based on 10,000 simulations of hypothetical trials under different assumptions of true response rates.

Table 2 Frequentist Properties of the Stopping Rules

True Response Rate	Pr (Stop Early)	Median Sample Size
0.05	0.92	17.7
0.1	0.35	27.9
0.15	0.32	35.6
0.2	0.16	40.2
0.25	0.07	42.6
0.3	0.03	43.9

We used MultLean software for the design of this trial. (<http://biostatistics.mdanderson.org/SoftwareDownload/>)

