11.2. Sample Size/Accrual Rate

We plan 12-15 months of accrual for 45 patients (approximately 3-4 patients per month) and a minimum of 6 months follow-up.

Evaluable patients include study subjects who received at least one cycle of HD IL-2 and had later formal imaging and clinical assessment of tumor response to treatment and those who failed to return for imaging because of cancer specific death or clinical determination of progression. Non-evaluable subjects will be replaced.

With 45 evaluable subjects, we will have >90% power to declare a significant difference between an response rate of 20% or higher and 7% (the expected response rate of this population under standard care) by a 1-sided exact binomial test ($\alpha=0.1$).

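### No single success criterion is named at 45 evaluable patients: the exact test is met at 6 responses, while the 20% sentence, read literally, needs 9

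*Combined protocol and SAP*

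**What the plan says.** Four places bear on the final conclusion.

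- **Section 11.1, text.** "We would consider the HD IL-2 worth further investigation if a response rate of 20% is achieved". This is the only sentence that links a result to a recommendation. The section also sets the size: "The total accrual goal is 45 patients".
- **Section 11.1, Table 1.** The futility boundaries are headed "Stop the Accrual to if". The last row is 4 or fewer responses in 45 patients.
- **Section 11.2.** "With 45 evaluable subjects, we will have >90% power to declare a significant difference" between 20% or more and "7% (the expected response rate of this population under standard care"), tested "by a 1-sided exact binomial test" at alpha 0.1.
- **Section 11.3.3.** The response rate is to be estimated with exact 90% confidence limits. No test, null value or count is given.

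No place states how many responses out of 45 make a positive result.

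**The concern.** The trial has one arm and a binary primary endpoint, so the design comes down to one number: the count of responses at which the regimen is judged worth pursuing. That number is missing, and two statements that could supply it lead to different counts. If 6, 7 or 8 patients respond, one reader can report a significant result against 7%, and another can report that the 20% mark was missed. Both could cite the plan. The choice would then be made with the count already known.

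The stated power has a related problem. It belongs to the 6-response line alone and leaves out the futility monitoring that the same design applies from the tenth patient.

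**Working it through.** **Inputs.** From sections 11.1 and 11.2: n = 45 evaluable, null rate 7%, target 20%, one-sided exact test at alpha 0.1. From section 11.1: the printed Table 1; the posterior rule, which stops if Pr(p0 + 0.05 > p1) exceeds 0.85; priors Beta(70,930) and Beta(0.4,1.6); and no stopping before 10 patients.

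**1. Reproduce the stated power.** P(X ≥ r) = Σ C(45,k) p^k (1−p)^(45−k), summed over k from r to 45.

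| r | Alpha (p = 0.07) | Power (p = 0.20) |
|---|---|---|
| 5 | 0.205 | 0.962 |
| 6 | 0.092 | 0.910 |
| 7 | 0.036 | 0.823 |
| 8 | 0.012 | 0.703 |
| 9 | 0.0035 | 0.559 |

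The smallest r with alpha at or below 0.10 is 6. Its power of 0.910 reproduces the plan's >90% for a fixed 45 patients without stopping.

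**2. Literal reading of the 20% sentence.** 0.20 × 45 = 9. A rule of at least 9 has power 0.559 at a true 20%.

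**3. Size of the gap, fixed 45.** P(6 to 8 | 0.20) = 0.9098 − 0.5593 = 0.3505.

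**4. Size of the gap with futility stopping.** I carried the response count forward one patient at a time, f_n(x) = f_{n−1}(x)(1−p) + f_{n−1}(x−1)p, removing any x at or below the boundary for n = 10 to 44. Two boundaries are needed because the posterior rule does not give the printed table. The rule gives ≤0 at 10–18 patients, ≤1 at 19–30, ≤2 at 31–41 and ≤3 at 42–45.

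| | Posterior rule | Table 1 as printed |
|---|---|---|
| Reach 45, p = 0.20 | 0.845 | 0.585 |
| Reach 45 with ≥6, p = 0.20 | 0.807 | 0.573 |
| Reach 45 with ≥9, p = 0.20 | 0.527 | 0.417 |
| Reach 45 with 6–8 (difference) | 0.280 | 0.156 |
| 6–8 among trials reaching 45 | 0.280/0.845 = 0.33 | 0.156/0.585 = 0.27 |
| Reach 45 with ≥6, p = 0.07 | 0.069 | 0.035 |

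Table 2 of the plan gives 0.16 early stopping and a sample size of 40.2 at a true 20%. The posterior rule gives 0.155 and a mean of 40.2, so the plan's simulations appear to have used that rule. Table 1 as printed would stop 0.415 of such trials before 45.

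**5. The 45-patient row.** Accrual is complete at 45, so the row has nothing to stop. With 5 of 45 the result is not futile by either boundary (Table 1 stops at ≤4, the posterior rule at ≤3) and not significant (p = 0.205).

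**6. The reported interval.** The lower exact 90% limit p_L solves P(X ≥ x | p_L) = 0.05. It is 5.97% at 6/45 and 7.54% at 7/45. The interval therefore excludes 7% only from 7 responses, one more than the test needs, because it puts 0.05 in the lower tail against the test's 0.10.

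**The case against.** The best defence is that section 11.2 already fixes the rule. Test, null, sidedness, alpha and n are all given, and together they imply 6 of 45 and nothing else. The context also suggests that 20% is a true rate: section 11.1 describes operating characteristics for an effective regimen in those terms, Table 2 is indexed by true response rate, and section 11.2 uses 20% as the alternative. An observed-20% rule would have power 0.56, which cannot fit a claim of >90%.

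Much of this stands. The true-rate reading is the more coherent one, and the 9-response line exists only on the literal reading. But the test appears only in the sample-size justification and is absent from the analysis section. The count is never printed. The one sentence on what makes the regimen worth pursuing speaks of a rate being achieved, which is how people describe an observed result.

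A reader might go further and infer three competing lines for a positive result (5, 6 and 9), in conflict in about 40% of full-size trials. The documents do not support that. Table 1 is a futility table, and nothing says that clearing it means success; a result that is neither futile nor significant is inconclusive, not contradictory. The 40% is 0.9618 − 0.5593 = 0.4025, the chance of 5 to 8 responses in a fixed 45-patient trial. Among trials that survive monitoring to 45 it is 37% (posterior rule) or 28% (Table 1).

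**Conclusion.** The point holds as an unresolved conflict between two candidate success criteria, 6 of 45 and 9 of 45, with a separate futility line that is not a success rule. At a true 20% rate, the conflict zone of 6 to 8 responses holds 35% of fixed 45-patient trials and 27% to 33% of those that reach 45 under monitoring. It does not follow that the conclusion is wholly open: the prespecified test points clearly to 6.

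The stated >90% power is right only without futility stopping. With stopping counted it is about 0.81 under the posterior rule and 0.57 under Table 1 as printed.

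These figures assume 45 evaluable patients, a futility check after every patient from the tenth with the response already known, and boundaries that are always obeyed. The size of the conflict also assumes that the 20% sentence can be read as an observed rate.

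**What to change.** 1. State in sections 11.1, 11.2 and 11.3.3 that HD IL-2 is worth further investigation if at least 6 of 45 evaluable patients respond (exact one-sided p = 0.092 against 7%).
2. Reword the 20% sentence so that it names a true response rate of 20% as the design alternative.
3. Remove the 45-patient row from Table 1, or label it as futility only.
4. Replace >90% with the power after futility stopping: about 0.81 if the posterior rule governs, 0.57 if Table 1 governs as printed. The plan must say which boundary applies. Give the matching false-positive rate at 7% (0.069 or 0.035).
5. Say in section 11.3.3 that the exact 90% interval is descriptive and is not the decision rule, since it excludes 7% only from 7 of 45.

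The cost is a few sentences and one table row. Sample size, eligibility and treatment do not change. The drawback is that the stated power becomes less favourable.
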